Appendix 4: Subject Satisfaction with Postsurgical Pain Control (Likert Scale)

Note: The subject's satisfaction with postsurgical pain control will be conducted at 72 hours after surgery and on Day 30.

Please circle the number below that best describes your overall satisfaction with the pain medication you received after surgery. (Circle one number only.)

1. Extremely dissatisfied
2. Dissatisfied
3. Neither satisfied nor dissatisfied
4. Satisfied
5. Extremely satisfied

Appendix 5: Physician's Satisfaction with Return of Sensory/Motor Function (Likert Scale)

Note: The physician's satisfaction with return of sensory/motor function will be assessed at 72 hours after surgery and on Day 30

Please circle the number below that best describes your overall satisfaction with the subject's return of sensory/motor function. (Circle one number only.)

1. Extremely dissatisfied
2. Dissatisfied
3. Neither satisfied nor dissatisfied
4. Satisfied
5. Extremely satisfied

Appendix 6: Opioid-Related Adverse Events Questionnaire

The opioid-related adverse events questionnaire will be completed at 72 hours after surgery during Part 1 only. The subject will be asked the questions below.

Since your operation, have you had:

[figure not shown]
- Itching all over your body? Yes No
- Excessive tiredness? Yes No
- Difficulty breathing? Yes No
- Did you need a postsurgical bladder catheter? Yes No
- Vomiting? Yes No
- Need for medicine to prevent vomiting? Yes No
- Constipation? Yes No
- Confusion? Yes No
- Delirium? Yes No

If the subject answers "Yes" to any of these questions, the event should be recorded as an AE.

Appendix 7: Dermatome Map

For the sensory function assessment, the subject's sensitivity in the innervated dermatomes (L2, L3) will be assessed at baseline, when the subject wakes up after surgery, and at 2, 4, 12, 24, 36, 48, 60, and 72 hours after surgery, or until the subject's sensitivity to cold has returned in two consecutive evaluations.

The subject's skin will be wiped with ice or an alcohol pad. The subject will then be asked, "Does this feel cold - yes or no?"

Site-Specific Addendum to Clinical Study Protocol Amendment 1

[figure not shown]
A Multicenter, Randomized, Double-Blind, Parallel-Group, Placebo-Controlled, Dose-Ranging Study to Evaluate the Safety, Efficacy, and Pharmacokinetics of Single Injection Femoral Nerve Block with Liposome Bupivacaine for Postsurgical Analgesia in Subjects Undergoing Total Knee Arthroplasty

Protocol No.: 402-C-323
EudraCT No.: N/A
IND No.: 69,198
Study Phase: 2/3
Study Drug: Liposome bupivacaine
Date: 14 January 2013
Study Site: Site 001
Investigator: [name]
Sponsor: Pacira Pharmaceuticals, Inc.
[name]
[contact]

Confidentiality Statement

The information contained in this document is confidential and the property of Pacira Pharmaceuticals, Inc. It should not be reproduced, revealed, or sent to third parties other than Institutional Review Boards/Independent Ethics Committees and the Investigator's research support staff participating in the conduct of the study without the prior written authorization of Pacira Pharmaceuticals, Inc.

SIGNATURE PAGE

 _____ [name] Executive Medical Director	_____ 14 January 2013 Date
 _____ [name] Chief Medical Officer	_____ 14 January 2013 Date
 _____ [name] Executive Director, Regulatory Affairs	_____ 14 January 2013 Date

Pharmacokinetic Assessments

Per protocol amendment 1, blood samples for pharmacokinetic (PK) analysis are to be collected from subjects at specific sites during Part 1 of the study at baseline, 15 minutes, 30 minutes, and 1, 2, 4, 8, 12, 24, 36, 48, 60, and 72 hours after the beginning of study drug administration.

Per this protocol addendum, additional blood draws for PK analysis may be collected from a subset of up to 20 subjects across two or more WIRB sites at 84, 96, 120, 144, 168 hours after the beginning of study drug administration, and on Day 10. The exact timing of the extra blood draws may be modified based on a review of the data by an unblinded statistician and pharmacokineticist. After a subject has been discharged from the hospital, the blood samples may be collected on an outpatient basis at the site or by a home healthcare agency designated by the study staff.

INVESTIGATOR AGREEMENT

Printed Name of Investigator: _____

Printed Title/Position: _____

Printed Institution Address: _____

I have reviewed this protocol (including Appendices) and agree:

- To assume responsibility for the proper conduct of the study at this site;
- To conduct the study in compliance with this protocol, with any future amendments, and with any other study conduct procedures provided by Pacira Pharmaceuticals, Inc. (Pacira) or designee. I also agree to comply with Good Clinical Practice and all regulatory requirements;
- Not to implement any changes to the protocol without agreement from Pacira or designee and prior review and written approval from the Independent Ethics Committee, except where it is necessary to eliminate an immediate hazard to the subjects or for administrative aspects of the study (where permitted by applicable regulatory requirements);
- That I am thoroughly familiar with the appropriate use of the investigational product(s), as described in this protocol, and with other relevant information (e.g., the Investigator's Brochure);
- To ensure that all persons assisting me with the conduct of this study are adequately informed about the investigational product(s) and about their study-related duties and functions as described in this protocol;

Per this protocol addendum, additional blood draws for PK analysis may be collected from a subset of up to 20 subjects across two or more WIRB sites at 84, 96, 120, 144, 168 hours after the beginning of study drug administration, and on Day 10. The exact timing of the extra blood draws may be modified based on a review of the data by an unblinded statistician and pharmacokineticist. After a subject has been discharged from the hospital, the blood samples may be collected on an outpatient basis at the site or by a home healthcare agency designated by the study staff.

INVESTIGATOR AGREEMENT

Printed Name of Investigator: _____

Printed Title/Position: _____

Printed Institution Address: _____

I have reviewed this protocol (including Appendices) and agree:

- To assume responsibility for the proper conduct of the study at this site;
- To conduct the study in compliance with this protocol, with any future amendments, and with any other study conduct procedures provided by Pacira Pharmaceuticals, Inc. (Pacira) or designee. I also agree to comply with Good Clinical Practice and all regulatory requirements;
- Not to implement any changes to the protocol without agreement from Pacira or designee and prior review and written approval from the Independent Ethics Committee, except where it is necessary to eliminate an immediate hazard to the subjects or for administrative aspects of the study (where permitted by applicable regulatory requirements);
- That I am thoroughly familiar with the appropriate use of the investigational product(s), as described in this protocol, and with other relevant information (e.g., the Investigator's Brochure);
- To ensure that all persons assisting me with the conduct of this study are adequately informed about the investigational product(s) and about their study-related duties and functions as described in this protocol;

1. LIST OF ABBREVIATIONS

AE	Adverse event
ANCOVA	Analysis of covariance
ANOVA	Analysis of variance
ASA	American Society of Anesthesiologists
ATC	Anatomic therapeutic chemical
AUC	Area under the curve
$AUC_{(0-inf)}$	Area under the plasma concentration versus time curve from time 0 extrapolated to infinity after drug administration
$AUC_{(0-last)}$	Area under the plasma concentration versus time curve from time 0 to the last collection time after drug administration
BLOQ	Below the limit of quantification
CI	Confidence interval
C_{max}	The maximum observed plasma concentration obtained directly from the experimental data without interpolation
%CV	Coefficient of variation
CRF	Case report form
CSR	Clinical study report
eCRF	Electronic case report form
ECG	Electrocardiogram
EMA	European Medicines Agency
FDA	Food and Drug Administration
ICH	International Conference on Harmonisation
IV	Intravenous
λ_z	Apparent terminal elimination rate constant

LOCF	Last observation carried forward
LS	Least squares
MedDRA	Medical Dictionary for Regulatory Activities
NRS	Numeric rating scale
NRS-A	Numeric rating scale with activity
NRS-R	Numeric rating scale at rest
OBAS	Overall benefit of analgesia score
ORAE	Opioid-related adverse event
PCA	Patient-controlled analgesia
PK	Pharmacokinetic
PO	Oral
SAP	Statistical analysis plan
SD	Standard deviation
SOC	System organ class
TEAE	Treatment-emergent adverse event
TKA	Total knee arthroplasty
T _{max}	Time to maximum concentration
t _½	Half-life calculated from the apparent terminal elimination rate
WHO-DD	World Health Organization Drug Dictionary
wWOCF	Windowed worst observation carried forward

2. INTRODUCTION

This statistical analysis plan (SAP) describes the planned statistical analysis and reporting of the clinical study 402-C-323 titled “A Multicenter, Randomized, Double-Blind, Parallel-Group, Placebo-Controlled, Dose-Ranging Study to Evaluate the Safety, Efficacy, and Pharmacokinetics of Single Injection Femoral Nerve Block with Liposome Bupivacaine for Postsurgical Analgesia in Subjects Undergoing Total Knee Arthroplasty”.

The structure and content of this SAP provides sufficient detail to meet the requirements identified by the US Food and Drug Administration (FDA), European Medicines Agency (EMA), and International Conference on Harmonisation (ICH) of Technical Requirements for Registration of Pharmaceuticals for Human Use: Guidance on Statistical Principles in Clinical Trials [1]. All work planned and reported for this SAP will follow internationally accepted guidelines, published by the American Statistical Association [2] and the Royal Statistical Society [3], for statistical practice.

The purposes of this SAP are to:

- Outline the types of analyses and presentations of data that will form the basis for drawing conclusions to the study objectives and hypotheses outlined in the protocol.
- Explain in detail how the data will be handled and analyzed, adhering to commonly accepted standards and practices for Good Statistical Practice.

The planned analyses identified in this SAP may be included in clinical study reports (CSRs), regulatory submissions, or future manuscripts. Also, post-hoc exploratory analyses not necessarily identified in this SAP may be performed to further examine study data. Any post-hoc, or unplanned, exploratory analyses performed will be clearly identified as such in the final CSR.

The following documents were reviewed in preparation of this SAP:

- Protocol 402-C-323 Amendment 2 issued on 19 April 2013.
- Case report forms (CRFs) for Protocol 402-C-323.
- ICH Guidance on Statistical Principles for Clinical Trials (E9).

The reader of this SAP is encouraged to also read the clinical study protocol and other identified documents for details on the planned conduct of this study. Operational aspects related to collection and timing of planned clinical assessments are not repeated in this SAP unless relevant to the planned analyses.

A separate SAP will be written for the analysis of electrocardiogram (ECG) data.

3. STUDY OBJECTIVES

Part 1: The primary objectives of Part 1 are to (1) evaluate three dose levels of liposome bupivacaine versus placebo with respect to the magnitude and duration of the analgesic effect achieved following single dose injection femoral nerve block with liposome bupivacaine, and (2) select a single therapeutic dose of liposome bupivacaine from the three dose levels to be tested in Part 2.

Part 2: The primary objective of Part 2 is to compare the magnitude and duration of the analgesic effect of single injection femoral nerve block of a single dose level of liposome bupivacaine (selected from Part 1) with placebo (preservative-free normal saline for injection).

The secondary objectives are to evaluate additional efficacy parameters, characterize the pharmacokinetic (PK) profile of liposome bupivacaine when administered as a femoral nerve block, and further assess the safety profile of liposome bupivacaine.

4. STUDY OVERVIEW

This is a Phase 2/3, multicenter, randomized, double-blind, parallel-group, placebo-controlled, dose-ranging study in subjects undergoing primary unilateral total knee arthroplasty (TKA) under general or spinal anesthesia.

On Day 1, eligible subjects will be randomized to receive a single dose of study drug administered within 2 hours prior to the surgical procedure as a femoral nerve block.

All subjects will be required to remain in the study site for a minimum of 72 hours after the end of surgery for postsurgical assessments.

Part 1

During Part 1 of the study, approximately 100 subjects (25 per treatment arm) will be randomized to receive a single dose injection femoral nerve block with either one of three doses of liposome bupivacaine (67, 133, or 266 mg) or placebo in 20 mL under ultrasound guidance. Preservative-free normal saline will be added to the 67 mg and 133 mg doses of study drug to achieve a volume of 20 mL.

After all subjects have completed the 72-hour assessments in Part 1, an analysis will be conducted in order to select a single therapeutic dose from the three liposome bupivacaine dose levels tested. The dose selected was 266 mg.

Part 2

In Part 2 of the study, approximately 180 subjects (approximately 90 liposome bupivacaine and 90 placebo subjects) will receive a single dose injection femoral nerve block with the selected dose of liposome bupivacaine (i.e., 266 mg) or placebo in 20 mL under ultrasound guidance.

Postsurgical Rescue Medication

Subjects should only receive rescue medication upon request for pain control, as needed.

First Rescue Medication (IV Hydromorphone)

The first rescue medication will be intravenous (IV) hydromorphone 0.5 mg, which will be administered once via bolus only.

Second Rescue Medication (PCA and/or PO Opioid)

The second rescue medication will be a patient-controlled analgesia (PCA) pump administered opioid (morphine or hydromorphone). The PCA pump will be programmed to deliver either: (1) on-demand morphine or (2) on-demand hydromorphone boluses at a dose and lockout interval in accordance with the site's standard practice. If a subject's pain is excessive or pain control is inadequate, then the bolus dose may be adjusted according to local hospital practices.

Once a subject is able to tolerate oral (PO) medication, PO immediate-release oxycodone may be administered (but not more than 10 mg every 4 hours).

Third Rescue Medication (Conventional Bupivacaine HCl)

If a subject's pain is inadequately controlled by opioids, a third rescue, a femoral nerve block, consisting of conventional bupivacaine HCl at a concentration of 0.125% (1.25 mg/mL) at a rate of 8 mL per hour for up to 12 hours may be administered via the previously placed femoral nerve catheter.

Postsurgical Assessments

Postsurgical assessments will include pain intensity scores using the 0-10 point numeric rating scale (NRS) at rest (NRS-R) and NRS with activity (NRS-A) (where the prescribed activity is active knee flexion up to 45 degrees); use of supplemental opioid pain medication; neurological assessment; cardiac assessment (i.e., ECG recordings); sensory function assessment (i.e., cold test); motor function assessment (i.e., 20-meter walk test); vital signs; overall benefit of analgesia score (OBAS) questionnaire; subject satisfaction with postsurgical pain control; physician satisfaction with return of sensory/motor function; and an opioid-related adverse events (ORAEs) questionnaire in Part 1 only. Adverse events (AEs) will be recorded through Day 30. If a cardiac or neurological event occurs during Part 1 or Part 2 of the study that the Investigator believes may be associated with high levels of systemic bupivacaine, an unscheduled PK blood sample should be collected at the time that the event is noted.

Safety and efficacy assessments will be conducted at pre-specified time points after the end of surgery. A follow-up visit will be scheduled for all subjects on Day 30.

See Table 1 in the protocol for the times of each of the assessments.

Pharmacokinetic Assessments (Part 1 only)

Blood samples for PK analysis will be obtained from subjects at specific sites during Part 1 of the study at baseline, 15 minutes, 30 minutes, and 1, 2, 4, 8, 12, 24, 36, 48, 60, and 72 hours after the beginning of study drug administration.

At two sites, there was an addendum to the protocol that allowed for additional blood draws for PK analysis from up to 20 subjects at 84, 96, 120, 144, 168 hours after study drug administration, and on Day 10.

Unscheduled blood samples also may be collected during Part 1 or Part 2 of the study if a cardiac or neurological event occurs that the Investigator believes may be associated with high levels of systemic bupivacaine.

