12.4. Pharmacokinetic Endpoints

Pharmacokinetic parameters are to be estimated from the plasma bupivacaine concentration-time profiles by non-compartmental analysis and are to include the following:

$AUC_{0-t_{last}}$ The area under the plasma concentration-time curve from the time of administration to the time of the last quantifiable concentration calculated using the lin/log trapezoidal rule.

$AUC_{0-\infty}$	The area under the plasma concentration-time curve from the time of administration extrapolated to infinity. The residual area from the time of the last quantifiable concentration ($C_{t_{last}}$) to infinity is to be calculated using the approximation: $AUC_{t-\infty} = C_{t_{last}} / \lambda_z$.
C_{max}	The maximum observed plasma concentration obtained directly from the experimental data without interpolation.
T_{max}	The time to attain C_{max} .
λ_z	The apparent terminal elimination rate constant determined by log-linear regression of the terminal log-linear segment of the plasma concentration-time curve.
$t_{1/2el}$	The apparent terminal elimination half-life calculated as $0.693/\lambda_z$.

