7.7.2. Pharmacokinetic Concentrations and Variables

The analysis of the PK data will be based on the PK analysis set.

Bupivacaine plasma concentrations will be listed by treatment group, subject, nominal time, and actual time. Concentrations that are BLOQ will be indicated by BLOQ in this listing.

Plasma concentrations will be summarized by treatment at each time point. The following descriptive statistics will be presented for plasma concentrations obtained at each nominal time point: n, geometric mean, arithmetic mean, SD, %CV, minimum, median, and maximum.

Pharmacokinetic parameters will be summarized by treatment. Descriptive statistics for calculated PK parameters will include: n, arithmetic mean, SD, %CV, geometric mean, median, minimum and maximum values. Geometric mean will not be presented for T_{\max} . Values of %AUC extrapolated > 20% will be flagged in the listings.

Individual plasma concentration versus actual times will be plotted by treatment in linear and semi-logarithmic scale.

At the 15 minute time point, unbound bupivacaine will be evaluated. The percentage of unbound over the total (unbound/total*100) will be summarized for subjects who have both values.

7.8. Safety Analyses.

All summaries of the safety data will use the safety analysis set.

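### AUC0-last is summarised by dose over subjects sampled to 72 h and addendum subjects who may be sampled to Day 10, with no AUC over a common time span

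*SAP*

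**What the plan says.** SAP Section 4 sets the main Part 1 PK schedule from baseline to "12, 24, 36, 48, 60, and 72 hours after the beginning of study drug administration". The same section notes that at two sites an addendum allowed, besides a Day 10 sample, "additional blood draws for PK analysis from up to 20 subjects at 84, 96, 120, 144, 168 hours after study drug administration". The addendum bound with the protocol makes these draws optional: "additional blood draws for PK analysis may be collected from a subset of up to 20 subjects across two or more WIRB sites". It adds that "The exact timing of the extra blood draws may be modified based on a review of the data by an unblinded statistician and pharmacokineticist".

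The end point of AUC0-last is described in two ways. The SAP abbreviation list gives "Area under the plasma concentration versus time curve from time 0 to the last collection time after drug administration", and the protocol synopsis agrees with it. Protocol 12.4 instead gives "The area under the plasma concentration-time curve from the time of administration to the time of the last quantifiable concentration", and SAP 7.7.1 likewise takes the final concentration to be the last quantifiable one and sets post-dose values below the limit of quantification to missing.

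SAP 7.7.1 uses actual sampling times for all parameters and has no cut-off at 72 h. SAP Section 6 defines one PK analysis set, not divided by sampling schedule. SAP 7.7.2 states: "Pharmacokinetic parameters will be summarized by treatment". Table 14.2.3.2-1 lists Cmax, Tmax, AUC0-last, AUC0-inf and half-life by dose. Extrapolation above 20% is flagged in the listings only.

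**The concern.** An area that runs to each subject's last sample can be compared between groups only if the last sample falls at about the same time in each group. Here it falls at 72 h for most subjects and possibly as late as Day 10 for up to 20. Two subjects with identical concentration curves would then contribute different AUC0-last values because one gave more blood. Unless the addendum subjects fall evenly over the three doses, part of the difference between dose-group means reflects the sampling schedule and not exposure.

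Characterising the PK profile is a stated secondary objective, and this table is its main exposure summary. A reader could take a schedule effect for a departure from dose-proportional exposure.

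**Working it through.** The plan states no figure on this point to reproduce. The size depends on a half-life that the documents do not give, so it is shown over an assumed range.

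**Inputs from the documents**
- Main horizon: 72 h (SAP 4).
- Addendum horizon: Day 10. Day 1 is the dosing day (SAP 5), so Day 10 is 9 × 24 = 216 h.
- Addendum subjects: at most 20 (SAP 4).
- Part 1: about 100 subjects, 25 per arm (SAP 4).

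**Assumptions**
- Mono-exponential decline from time 0 with half-life h, taken as 8 to 48 h.
- All addendum draws taken and quantifiable to 216 h.
- About 25 PK-evaluable subjects per arm.

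**Step 1: effect in one subject.** With k = ln 2 / h, the ratio is R = AUC(0-216) / AUC(0-72) = (1 − e^(−216k)) / (1 − e^(−72k)). At h = 24 h, for example, R = (1 − 2^(−9)) / (1 − 2^(−3)) = 0.998 / 0.875 = 1.141.

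**Step 2: effect on a comparison of doses.** If a share f of an arm is in the addendum, the arm mean rises by f × (R − 1). Two arms whose shares differ by d then differ by about d × (R − 1) with no true difference in exposure.

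If 20 of 100 subjects fall at random over four arms of 25, the expected number per arm is 5 and the 95% range is 2 to 8 (hypergeometric). The median gap between the largest and smallest count among the three active arms is 3, so d = 3/25 = 0.12.

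| Assumed half-life | R | Spurious difference, 0.12 × (R − 1) |
|---|---|---|
| 8 h | 1.002 | 0.02% |
| 12 h | 1.016 | 0.2% |
| 24 h | 1.141 | 1.7% |
| 36 h | 1.312 | 3.7% |
| 48 h | 1.479 | 5.7% |

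**Step 3: sensitivity to the curve shape.** If concentration is flat for 48 h before it declines, R becomes 1.03 at 8 h, 1.07 at 12 h, 1.26 at 24 h, 1.46 at 36 h and 1.63 at 48 h. Slow release therefore raises the figures.

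**Step 4: after the fix.** AUC0-72 has the same end point for every subject, so the schedule-related difference is zero by construction.

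**The case against.** The best counter-argument is that the effect may be negligible and has little to act on.

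- **It is conditional.** The draws are optional. Under protocol 12.4 and SAP 7.7.1 the area extends past 72 h only while bupivacaine remains quantifiable, and no limit of quantification is given. This stands, and the point is stated conditionally for that reason. Under the abbreviation-list wording the horizon would extend whenever a sample was drawn, which is why the definitions need aligning.
- **Nothing formal depends on it.** The PK analysis is descriptive, with no between-dose test. The doses differ about 2-fold and 4-fold, so a shift of a few percent would not change the broad picture. The interim plan in SAP 7.9 passes on only the maximum Cmax. This stands too.
- **Other outputs help.** AUC0-inf does not mix fixed horizons, and the listings and individual plots show who was sampled late. This stands in part. For subjects sampled to 72 h, AUC0-inf relies more on extrapolation, and values with more than 20% extrapolated are only flagged.

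A reader might infer a larger effect, such as 4-9% between doses, by taking half-lives of 24-36 h and a split of 40% against 12% of an arm (10 against 3 of 25). The documents support neither choice. They give no half-life, and at 8-12 h the same split yields under 0.5% (0.28 × 0.016 = 0.4%). The split is also near worst case: under random allocation, a gap of 7 or more among the three active arms has a probability of about 5%.

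**Conclusion.** The point holds as a minor one. The SAP pools two sampling horizons in AUC0-last and plans no common-horizon AUC. Whether this shows in the results depends on the addendum draws being taken and on bupivacaine being quantifiable after 72 h.

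For a typical imbalance of 3 in 25, the spurious difference between doses is close to zero if the half-life is 12 h or less, about 2-4% at 24-36 h and about 6% at 48 h. These figures rest on mono-exponential decline and about 25 evaluable subjects per arm. A plateau before decline, or arms made smaller by exclusions for conventional bupivacaine rescue, would raise them. Sampling that ends before Day 10 would lower them.

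The documents do not support reading this as a threat to dose selection, to the efficacy results or to the interim Cmax review. They also do not show that the planned AUC0-last summaries will be materially wrong. The case for acting is that the size cannot be known from the plan and the remedy is almost free.

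**What to change.** 1. In SAP 7.7.1, add AUC0-72 for every subject in the PK set and name it as the AUC for comparing dose groups. State in one sentence how it is obtained when the last quantifiable sample falls before 72 h.
2. Add one AUC0-72 row to Table 14.2.3.2-1.
3. Align the AUC0-last entry in the SAP abbreviation list, and the matching line in the protocol synopsis, with the last-quantifiable-concentration definition in protocol 12.4 and SAP 7.7.1.
4. Keep AUC0-last, AUC0-inf and half-life as planned, with a footnote giving the number of extended-sampling subjects in each dose group.

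The cost is one partial-area setting in the PK software, one table row, one footnote and a wording correction; no new data are needed. Separate summaries of every parameter by sampling schedule are not recommended, because about 5 extended-sampling subjects per arm is too few for a stable SD or %CV.
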